12.4 Final Analysis

The database will be locked prior to the final analysis (FA) which will be conducted when all randomized subjects have reached Week 56 or terminated early. As described in [Section 12.3](#), all the efficacy endpoints will be tested in a hierarchical order, at the highest tolerated dose of IMR-687 vs placebo. If all the efficacy comparisons are successful, testing of the IMR-687 pooled dose vs. placebo, and of lower dose vs. placebo will be performed. Propagated alpha from the primary efficacy analysis at the IA will be used in the FA to maintain an overall type I error rate of 5% for 2-sided testing. After the first instance of a failure to reject the null hypothesis, p-values from all remaining comparisons will still be reported, but deemed nominal. The hierarchical order of testing of primary, key secondary and other secondary endpoints is:

1. Annualized rate of VOCs
2. Time to first VOC
3. HbF responder rate at Week 24
4. Proportion of VOC-free subjects
5. Annualized rate of VOC-related hospitalization
6. Annualized rate of days hospitalized for VOC-related hospitalizations
7. Time to second VOC
8. Change from baseline in key biomarkers of RBC hemolysis (indirect bilirubin and % reticulocytes) at Week 24 and Week 52
9. HbF responder rate at Week 52
10. Change from baseline in HbF (%) and F-cells (%) at Week 24 and Week 52
11. Hb responder rates at Week 24 and Week 52
12. Change from baseline in total Hb (g/dL) at Week 24 and Week 52
13. Change from baseline in other biomarkers of RBC hemolysis (absolute reticulocytes and lactate dehydrogenase [LDH]) at Week 24 and Week 52
14. Change from baseline in biomarkers of adhesion such as soluble E-selectin (E-sel), P-selectin (P-sel), intercellular adhesion molecule 1 (ICAM-1), and vascular cell adhesion molecule 1 (VCAM-1) at Week 24 and Week 52
15. Change from baseline in biomarkers of inflammation such as high-sensitivity C-reactive protein (hsCRP) and myeloperoxidase (MPO) at Week 24 and Week 52
16. Change from baseline in biomarkers of cardiac stress such as N-terminal prohormone of brain natriuretic peptide (NT-proBNP) at Week 24 and Week 52
17. Change from baseline in RBC indices, such as mean corpuscular volume (MCV) at Week 24 and Week 52
18. Change from baseline in each measured subdomain of ASCQ-Me questionnaire at Week 24 and Week 52
19. Change from baseline in total preference score and individual domain scores of PROPr questionnaire at Week 24 and Week 52

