The Adult Sickle Cell Quality of Life Measurement Information System (ASCQ-Me®) is a systemic, reliable, and valid method for documenting adult SCD patient-reported outcomes. The questions are grouped into 3 domains (physical, social, and emotional) encompassing 7 subdomains, of which the following 5 will be measured: emotional impact, pain impact, sleep impact, social functioning impact, and stiffness impact. Of note, pain episodes and frequency, and SCD medical history checklist will not be evaluated, but the reliability of the instrument should allow for use of only a subset of the validated domains. Each subdomain includes 5 to 9 items. Recall periods vary by subdomain and even question, with most of the periods being from 7 days to 30 days. Subdomain scores are standardized to have a mean of 50 and a standard deviation of 10.

Each of the five subdomains measured in this study consists of five questions. Responses to each question range in numeric value from 1 (Always/Very/Very much) to 5 (Never/Not at all). To calculate each subdomain score, responses to each of the 5 questions will be summed, and then converted to T-scores with standard errors (SE) based on the scales in [Appendix 1](#). If any question within a subdomain is not answered, the subdomain score will be missing for that subject/time point. Untransformed scores range from 5 to 25, and the range of converted scores depends on the subdomain. Higher scores indicate healthier status.

The analysis of change from baseline in each measured subdomain of the ASCQ-Me questionnaire at Week 24 and Week 52 will be based on an analysis of covariance (ANCOVA) model with fixed effects for treatment, visit, and treatment-by-visit interaction, and baseline value, region, and HU use as covariates. Mean (95% CI), Mean difference (95% CI), and p-value will be provided. The T-score analysis will be performed for each of the following parameters (subdomains), at Week 24 and Week 52 separately:

- Emotional Impact
- Pain Impact
- Sleep Impact
- Social Functioning Impact
- Stiffness Impact

Line plots will be provided for LS mean change +/- SE.

Change from baseline in total preference score and individual domain scores of the PROPr questionnaire at Week 24 and Week 52

The PROMIS-29+2 Profile (PROPr) questionnaire (version 2.1) consists of seven domain scores (Physical Function, Anxiety, Depression, Fatigue, Sleep Disturbance, Ability to Participate in Social Roles

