and Activities, and Pain Interference), as well as a Cognitive Function short form and a Pain Intensity question. Each domain consists of four questions. Responses to each question range in numeric value from 1 (Unable to do/Never/Not at all/Very poor) to 5 (Without any difficulty/Always/Very much/Very good). The Cognitive Function short form consists of two questions where responses range from 1 (Not at all) to 5 (Very much). To calculate each domain score and cognitive function score, responses to each of the 4 questions (or 2 questions for the cognitive function) will be summed, and then converted to T-scores with SE based on the scales in [Appendix 2](#). If any question within a domain is not answered the domain score will be missing for that subject/time point. Untransformed scores range from 4 to 20, and the range of converted T-score depends on the domain. Higher scores indicate a healthier status.

The total preference (PROPs) score will be calculated using SAS codes provided in Appendix 1 of “The Development of a Preference-based Scoring System for PROMIS (PROPr): A Technical Report (v1.4)” by [Hanmer and Dewitt](#) (December 2017). The PROPs score is between 0 and 1 with higher scores indicating better quality of life.

The analysis of change from baseline in total preference score and individual domain T-scores of the PROPr questionnaire at Week 24 and Week 52 will be similar to the analysis of ASCQ-Me. The analysis will be performed for each of the following parameters, at Week 24 and Week 52 separately:

- Total Preference Score
- Physical Function
- Anxiety
- Depression
- Fatigue
- Sleep Disturbance
- Ability to Participate in Social Roles and Activities
- Pain Interference
- Cognitive Function
- Pain Intensity

Line plots will be provided for LS mean change +/- SE.

Change from baseline in overall score of the SCSES at Week 24 and Week 52

The Sickle Cell Self-Efficacy Scale (SCSES) is a 9-item QoL measure for adults with SCD. This measure is a self-appraisal of an SCD patient's ability to engage in daily functional activities and to manage SCD symptomatology. Response choices range from “not at all sure” to “very sure”. Responses from individual items are summed to give an overall score with higher scores indicating greater self-efficacy for coping with SCD. If the response for any of the individual questions is missing, the overall score will be missing.

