Appendix 2 PROMIS-29+2 Profile v2.1 (PROPr) Scoring Tables

| Adult v2.0 - Physical Function 4a | | |
|-----------------------------------|---------|-----|
| Short Form Conversion Table | | |
| Raw Summed Score | T-score | SE* |
| 4 | 22.5 | 4.0 |
| 5 | 26.6 | 2.8 |
| 6 | 28.9 | 2.5 |
| 7 | 30.5 | 2.4 |
| 8 | 31.9 | 2.3 |
| 9 | 33.2 | 2.3 |
| 10 | 34.4 | 2.3 |
| 11 | 35.6 | 2.3 |
| 12 | 36.7 | 2.3 |
| 13 | 37.9 | 2.3 |
| 14 | 39.2 | 2.4 |
| 15 | 40.5 | 2.4 |
| 16 | 41.9 | 2.5 |
| 17 | 43.5 | 2.6 |
| 18 | 45.5 | 2.8 |
| 19 | 48.3 | 3.3 |
| 20 | 57.0 | 6.6 |

*SE = Standard Error on T-score metric

| Adult v1.0 - Anxiety 4a | | |
|-----------------------------|---------|-----|
| Short Form Conversion Table | | |
| Raw Summed Score | T-score | SE* |
| 4 | 40.3 | 6.1 |
| 5 | 48.0 | 3.6 |
| 6 | 51.2 | 3.1 |
| 7 | 53.7 | 2.8 |
| 8 | 55.8 | 2.7 |
| 9 | 57.7 | 2.6 |
| 10 | 59.5 | 2.6 |
| 11 | 61.4 | 2.6 |
| 12 | 63.4 | 2.6 |
| 13 | 65.3 | 2.7 |
| 14 | 67.3 | 2.7 |
| 15 | 69.3 | 2.7 |
| 16 | 71.2 | 2.7 |
| 17 | 73.3 | 2.7 |
| 18 | 75.4 | 2.7 |
| 19 | 77.9 | 2.9 |
| 20 | 81.6 | 3.7 |

*SE = Standard Error on T-score metric

| Adult v1.0 - Depression 4a | | |
|-----------------------------|---------|-----|
| Short Form Conversion Table | | |
| Raw Summed Score | T-score | SE* |
| 4 | 41.0 | 6.2 |
| 5 | 49.0 | 3.2 |
| 6 | 51.8 | 2.7 |
| 7 | 53.9 | 2.4 |
| 8 | 55.7 | 2.3 |
| 9 | 57.3 | 2.3 |
| 10 | 58.9 | 2.3 |
| 11 | 60.5 | 2.3 |
| 12 | 62.2 | 2.3 |
| 13 | 63.9 | 2.3 |
| 14 | 65.7 | 2.3 |
| 15 | 67.5 | 2.3 |
| 16 | 69.4 | 2.3 |
| 17 | 71.2 | 2.4 |
| 18 | 73.3 | 2.4 |
| 19 | 75.7 | 2.6 |
| 20 | 79.4 | 3.6 |

*SE = Standard Error on T-score metric

| Adult v1.0 - Fatigue 4a | | |
|-----------------------------|---------|-----|
| Short Form Conversion Table | | |
| Raw Summed Score | T-score | SE* |
| 4 | 33.7 | 4.9 |
| 5 | 39.7 | 3.1 |
| 6 | 43.1 | 2.7 |
| 7 | 46.0 | 2.6 |
| 8 | 48.6 | 2.5 |
| 9 | 51.0 | 2.5 |
| 10 | 53.1 | 2.4 |
| 11 | 55.1 | 2.4 |
| 12 | 57.0 | 2.3 |
| 13 | 58.8 | 2.3 |
| 14 | 60.7 | 2.3 |
| 15 | 62.7 | 2.4 |
| 16 | 64.6 | 2.4 |
| 17 | 66.7 | 2.4 |
| 18 | 69.0 | 2.5 |
| 19 | 71.6 | 2.7 |
| 20 | 75.8 | 3.9 |

*SE = Standard Error on T-score metric

| Adult v1.0 - Sleep Disturbance 4a | | |
|-----------------------------------|---------|-----|
| Short Form Conversion Table | | |
| Raw Summed Score | T-score | SE* |
| 4 | 32.0 | 5.2 |
| 5 | 37.5 | 4.0 |
| 6 | 41.1 | 3.7 |
| 7 | 43.8 | 3.5 |
| 8 | 46.2 | 3.5 |
| 9 | 48.4 | 3.4 |
| 10 | 50.5 | 3.4 |

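### SAP 13.5.4 says higher PROPr domain scores are healthier, but its own coding and tables make higher scores worse for at least four symptom domains

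*SAP*

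**What the plan says.** SAP 13.5.4 describes the PROPr items in one sentence for all four-item domains: "Responses to each question range in numeric value from 1 (Unable to do/Never/Not at all/Very poor) to 5 (Without any difficulty/Always/Very much/Very good". The responses in each domain "will be summed, and then converted to T-scores with SE based on the scales in" Appendix 2. No item or domain is reverse-scored, either there or in the appendix. The paragraph then says "Untransformed scores range from 4 to 20" and closes with "Higher scores indicate a healthier status", without exceptions.

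The total preference score has its own statement: "The PROPs score is between 0 and 1 with higher scores indicating better quality of life". Pain Intensity is listed apart from the domains as a single question. Appendix 2 gives it no T-score conversion (scale 0-10), and no direction is stated for it.

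The preceding text on ASCQ-Me has almost the same direction sentence, but its items are coded the other way round: "from 1 (Always/Very/Very much) to 5 (Never/Not at all".

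The PROPr scores are formal secondary endpoints. Step 19 of the hierarchy in SAP 12.4 is "Change from baseline in total preference score and individual domain scores of PROPr questionnaire at Week 24 and Week 52", and each parameter is tested separately.

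**The concern.** If Never or Not at all scores 1 and Always or Very much scores 5, adding up the items of a symptom scale gives a number that grows with the symptom. A sentence calling the higher number healthier is then backwards for that scale, unless items are reverse-scored or the conversion table runs downwards. The ASCQ-Me coding makes the sentence correct for that instrument; it may have been carried over to PROPr, though that is an inference.

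What is at stake is how results are read. The sentence is the only guidance the documents give on whether a difference in a PROPr domain is benefit or harm. A reader who follows it would describe fewer anxiety symptoms on IMR-687 as a decline, and more symptoms as a gain. The late place in the hierarchy does not keep this out of the report. Under SAP 12.4, p-values after a failed step are still reported as nominal, and SAP 13.5.4 plans plots of LS mean change for these parameters.

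**Working it through.** **Inputs.** Response codes, scoring rule and parameter list: SAP 13.5.4. Raw-to-T conversion: Appendix 2. Order of testing: SAP 12.4.

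**Step 1: reproduce the stated raw range.** Four items coded 1 to 5 give 4 × 1 = 4 up to 4 × 5 = 20, as the SAP says. This confirms a plain sum. (The two-item Cognitive Function form gives 2 × 1 = 2 to 2 × 5 = 10, as its own table shows, so the 4-to-20 statement does not cover it.)

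**Step 2: do the tables reverse the direction?** All seven four-item tables were checked. In each, the T-score rises strictly with the raw score; none is inverted. In the table headed "Adult v1.0 - Anxiety 4a", for example, raw 4 gives 40.3 and raw 20 gives 81.6.

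**Step 3: apply the SAP's rule to a symptom reduction.** Take a fall from raw 12 to raw 8; change = T(8) − T(12).

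| Domain | T at raw 4 | T at raw 20 | T(12) | T(8) | Change | Meaning under the coding | Meaning under the SAP sentence |
|---|---|---|---|---|---|---|---|
| Anxiety | 40.3 | 81.6 | 63.4 | 55.8 | −7.6 | better | worse |
| Depression | 41.0 | 79.4 | 62.2 | 55.7 | −6.5 | better | worse |
| Fatigue | 33.7 | 75.8 | 57.0 | 48.6 | −8.4 | better | worse |
| Pain Interference | 41.6 | 75.6 | 61.2 | 55.6 | −5.6 | better | worse |
| Sleep Disturbance | 32.0 | 73.3 | 54.3 | 46.2 | −8.1 | better, if read by scale name | worse |

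For Physical Function (Unable to do = 1, Without any difficulty = 5) a higher score is healthier, and the sentence is right.

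**Step 4: count the tests affected.** SAP 13.5.4 lists ten PROPr parameters, analysed at two visits: 10 × 2 = 20 tests for a given treatment comparison.

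- Reversed on the printed anchors: 4 domains × 2 visits = 8 of 20.
- Adding Sleep Disturbance by its scale name: 5 × 2 = 10 of 20.
- Pain Intensity: not counted, because the sentence follows text on summed, T-converted domain scores and is best read as not covering it.

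**Step 5: how many tests come first at the final analysis?** SAP 12.4 counts each endpoint and visit separately. Steps 1-7 give 7, and steps 8 to 18 give 4, 1, 4, 2, 2, 4, 8, 4, 2, 2 and 10. The total is 7 + 43 = 50 tests that must all succeed before the first PROPr test counts formally.

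**The case against.** The strongest reply is that the sentence is only descriptive. No scoring step, model, imputation rule or SAS template uses it. The tests are two-sided, so p-values, LS means and confidence intervals do not depend on it. Outputs will carry names such as Anxiety and Depression, and few readers would take a rise in those for good news. About 50 earlier tests must succeed before a PROPr result counts formally. All of this stands, and it limits the consequence to possible misreading.

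The second reply concerns scope. The anchors also include Very poor = 1 and Very good = 5, and the items are not printed. A sleep item with those anchors would run in the healthy direction unless reverse-scored, so Sleep Disturbance is not proven reversed by the printed coding. This stands too. So does the same caution for Social Roles, where the printed anchors do not settle the direction.

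A reader might go further and infer that the sentence lets a significant worsening pass a step of the fixed sequence. The documents do not support blaming the sentence for that. SAP 13.5.2.2 asks for a result in favour of IMR-687 only for the primary endpoint; later steps require only rejection of the null hypothesis. That gap would remain if the sentence were corrected. A reader might also count 12 of 20 tests as reversed by adding Pain Intensity, but for that item the direction is missing, not misstated.

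None of this rescues the sentence for Anxiety, Depression, Fatigue and Pain Interference. Nothing elsewhere in the SAP corrects it, and protocol 11.2.4 gives no PROPr direction.

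**Conclusion.** Wrong as written. The SAP's only direction rule for PROPr domain scores contradicts its own coding, summing and tables for four domains, or 8 of 20 PROPr tests. With Sleep Disturbance read by its scale name the figure is 10 of 20. Pain Intensity is a separate gap.

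The effect is on interpretation: improvement in these domains could be reported as worsening, and the reverse, in nominal results and LS mean plots as well as in any formal claim. It is not established that results would be misreported. Two-sided p-values, the size of the differences, the preference score and the primary and key secondary endpoints do not change.

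This rests on two assumptions: that scoring follows the text, with no unstated reverse scoring, and that the printed Never/Not at all and Always/Very much anchors apply to the four named symptom scales.

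**What to change.** Replace the single sentence in SAP 13.5.4 with a direction for each score:

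- Higher is worse: Anxiety, Depression, Fatigue, Pain Interference and Sleep Disturbance.
- Higher is better: Physical Function, Cognitive Function and the total preference score.
- Sleep Disturbance and Social Roles: confirm item-level coding against the instrument before summing, and record any reverse-scored items. State the Social Roles direction once confirmed.
- Pain Intensity: state the direction.

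Add that a PROPr step counts as passed only when the difference favours IMR-687 in the stated direction. Make the change before database lock. It alters wording only, with no effect on data, alpha or timeline, and has no downside.

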13.5.5 Exploratory Efficacy Endpoints

The analysis of change (and percentage change) from baseline in renal function at Week 24 and Week 52 will be similar to the analysis of other change from baseline efficacy variables. Change from baseline will be calculated for each of the following renal function parameters at Week 24 and Week 52 separately:

- Urine protein-to-creatinine (Pr:Cr) ratio
 - Urine Microalbumin
 - Urine ACR (albumin to creatinine ratio)
- Urine Cystatin C

Line plots will be provided for LS mean change +/- SE.

Additional exploratory analysis (which are not specified in protocol) will be performed if the data allow, as shown in, but not limited to, the list below. In general, the exploratory endpoints will be analyzed following the same analysis approach specified for similar endpoints specified in primary and secondary analysis sections at FA, unless otherwise specified.

VOC Analyses:

- Number and percentage of subjects with at least 1 VOC event

- Number and percentage of subjects by category of number of VOC events: 0, 1, 2-4, 5-7, 8-12, 13+
- Number of and percentage of subjects with at least one VOC event lasting for \geq 48 hours
- Number and percentage of subjects with complicated VOCs (ACS, priapism, hepatic or splenic sequestration)
 - Number and percentage of subjects with at least 1 ACS
 - Number and percentage of males with priapism
 - Number and percentage of subjects with hepatic or splenic sequestration
- Number of and percentage of subjects with uncomplicated VOCs
- Time to first event of complicated VOCs
- Annualized rate of days of VOCs (days)
- Annualized VOC rate, excluding subjects with a short period of exposure (< 4 weeks)
- Annualized rate of uncomplicated VOCs

VOC-Related Hospitalizations:

- Number and percentage of subjects with at least 1 VOC-related hospitalization
- Number and percentage of subjects by category of number of VOC-related hospitalizations: 0, 1, 2-4, 5-7, >7.

RBC Transfusions:

- Time to first RBC transfusion
- Number and percentage of subjects with at least 1 RBC Transfusion

Relationships between biomarkers

- Pairwise correlation (Pearson correlation coefficients and p-values) of annualized rate of VOCs and PD parameters (e.g., HbF, Total Hb, F-cells) will be tabulated for Week 24 and Week 52, and for HU and non-HU use separately and together. Corresponding scatter plots will also be provided.

13.5.6 Subgroup Analyses

The following subgroups will be assessed based on the primary, key secondary and PD endpoints (HbF, Hb and F-cells). All subgroup analyses will be performed for each subgroup level. Summary tables and a forest plot will display descriptive statistics for each level of a subgroup for a population.

- Age (\leq median and $>$ median of the total population)
- Sex (Female vs Male)
- Region (North America/Europe vs Africa/Middle East)
- Baseline HU use (Yes vs No)
- Baseline number of VOCs (1, 2-4, 5-12)
- Baseline number of VOCs (1, 2-12) [VOC analysis only]

- Baseline HbF (\leq median and $>$ median of the total population)
- Baseline Hb (\leq median and $>$ median of the total population)

Baseline HU use are based on the randomization stratum used in IRT. The actual baseline HU use from Prior and Concomitant Medications CRF page may be used to perform additional subgroup analysis, if they are not same.

Summary tables and forest plots will be produced to show the treatment difference in the overall population and also within each subgroup. The statistics shown will depend on the type of analysis:

1. Relative risk for the annualized rate of VOCs
2. Log-rank and Cox Proportional hazards from the time to event
3. Percentage of responders from responder analysis (HbF and Hb)
4. LS Mean from MMRM analysis (HbF, Hb, F-cells)

Statistical models will be used to test if the difference between treatments differs between each level of a subgroup (i.e., to test the treatment-by-subgroup interaction).

It should be noted that the study was not designed to detect treatment differences with high statistical power within subgroups. If any subgroup level includes $< 5\%$ of all subjects, no inferential statistics will be generated.

13.5.7 Multiplicity Adjustment

A fixed-sequence statistical strategy tests endpoints in a predefined order, all at the same significance level alpha (e.g., $\alpha = 0.05$), moving to a second endpoint only after a success on the previous endpoint. Such a test procedure does not inflate the Type I error rate as long as there is (1) prospective specification of the testing sequence and (2) no further testing once the sequence breaks, that is, further testing stops as soon as there is a failure of an endpoint in the sequence to show significance at level alpha (e.g., $\alpha = 0.05$).

Fixed-sequence statistical strategy for multiplicity adjustment will be used in this study. Endpoints will be tested using $\alpha = 0.05$. The fixed sequence for endpoint testing will follow the order prescribed in section 12.4.

13.5.8 Safety Analyses

In general, safety analyses will be based on the safety analysis set and will be provided by treatment group as defined in [Section 11.1](#). The "Total" column will not be included in the summary tabulations.

Visit windowing (as specified in [Section 10.5](#)) will be used to determine the analysis visit for laboratory, vital sign and ECG by-visit analyses.

13.5.8.1 Adverse Events

MedDRA Coding

AEs will be coded using MedDRA (v23.0 or higher).

Treatment-emergent adverse event (TEAE)

A treatment-emergent adverse event (TEAE) is defined as an AE that emerges on or after initiation of study drug, or an AE that existed pre-treatment and worsened in severity on or after initiation of study drug, through 30 days after the last dose of study drug. A pre-treatment adverse event is an AE emerges before the initiation of study drug.

Refer to [Appendix 4](#) for handling of partial dates for AEs for the purpose of identifying treatment-emergent AEs. In the case where it is not possible to define an AE as treatment-emergent or not, the AE will be classified as treatment-emergent.

Severity

Severity is classified as Grade 1: Mild, Grade 2: Moderate, Grade 3: Severe, Grade 4: Life-Threatening, Grade 5: Death Related to AE, using the Common Terminology Criteria for Adverse Events, v5.0 (CTCAE v5.0). For the AE summary by CTCAE severity grade, an AE with missing CTCAE severity grade will not be imputed.

Relationship to Study Treatment

Relationship is classified as “Unlikely/Not related”, “Possible”, “Probably/Likely”, or “Certain/Related” by the Investigator. A “treatment-related TEAE” for the purpose of this summary is defined as a TEAE with relationship to study drug of “Possible”, “Probably/Likely” or “Certain/Related”. For the AE summary by relationship, an AE with a missing relationship to study drug will not be imputed. Imputed values will not be included in data listings.

TEAEs Leading to Discontinuation of Study Treatment

TEAEs leading to discontinuation of study treatment will be identified by action taken with study treatment being recorded as “Drug withdrawn” on the Adverse events CRF.

Serious and Non-Serious TEAEs

Serious adverse events (SAEs) are those events recorded as “Yes” for the question “Was the adverse event serious?” on the Adverse Event CRF.

TEAEs Leading to Death

TEAEs leading to death are those events which are recorded as “Yes” for the question “Did the adverse event result in death?”, or recorded CTCAE Toxicity Grade 5, or with outcome = “Fatal” on the Adverse Events CRF.

TEAEs Leading to Study Discontinuation

TEAEs leading to study discontinuation are those events which are recorded as “Yes” for the question “Did the adverse event cause the subject to be discontinued from the study?” on the Adverse events CRF.

TEAEs Leading to Dose Reduction

TEAEs leading to dose reduction will be identified by action taken with study treatment being recorded as “Dose Reduced” on the Adverse events CRF.

Overall Summary

An overall summary of TEAEs will be presented by treatment group for the safety analysis set. The number and percentage of subjects reporting any of the following categories will be provided:

- Any pre-treatment adverse event
- Any TEAE
- Grade 3 or higher TEAEs
- Treatment-related TEAEs
- Treatment-related grade 3 or higher TEAEs
- Treatment-related grade 2 or higher TEAEs
- SAEs
- Treatment-related SAEs
- Treatment-related grade 3 or higher SAEs
- TEAEs leading to death

- TEAEs leading to discontinuation of study drug
- Treatment-related TEAEs leading to discontinuation of study drug
- TEAEs leading to study discontinuation
- Treatment-related TEAEs leading to study discontinuation
- TEAEs leading to dose reduction
- Treatment-related TEAEs leading to dose reduction

The following AE summaries will be by treatment group, SOC and PT for the safety analysis set. SOCs will be sorted alphabetically and PTs will be sorted by descending frequency in the pooled IMR-687 treatment group column, and then alphabetically for ties.

- The number and percentage of subjects with any TEAE. The AE count will be for subjects not events, and subjects are only counted once within each SOC or PT
- The number and percentage of subjects with Grade 3 or higher TEAEs
- The number and percentage of subjects with Treatment-related TEAEs. Subjects with multiple events within a particular SOC or PT will be counted under the category of their most drug-related event within that SOC or PT (related or not related). AEs will be considered related to study drug if they are reported as certain/related, probably/likely related, or possibly related.
- The number and percentage of subjects with Treatment-related TEAEs
- The number and percentage of subjects with Treatment-related Grade 3 or higher TEAEs
- The number and percentage of subjects with Treatment-related Grade 2 or higher TEAEs
- The number and percentage of subjects with SAEs
- The number and percentage of subjects with Treatment-related SAEs
- The number and percentage of subjects with Treatment-related Grade 3 or higher SAEs
- The number and percentage of subjects with TEAEs leading to death
- The number and percentage of subjects with TEAEs leading to discontinuation of study drug
- The number and percentage of subjects with Treatment-related TEAEs leading to discontinuation of study drug
- The number and percentage of subjects with TEAEs leading to study discontinuation
- The number and percentage of subjects with Treatment-related TEAEs leading to study discontinuation
- The number and percentage of subjects with TEAEs leading to dose reduction
- The number and percentage of subjects with Treatment-related TEAEs leading to dose reduction
- The number and percentage of subjects with TEAEs by severity. Subjects with multiple events within a particular SOC or PT will be counted under the category of their most severe event within that SOC or PT. AE severity (intensity) will be graded using NCI CTCAE, version 5.0.

- The number and percentage of subjects with TEAEs by relationship. Subjects with multiple events within a particular SOC or PT will be counted under the category of their most related event within that SOC or PT.

The following AE tables will be summarized by treatment group (without a “Total” column) and PT for the safety analysis set. PTs will be sorted by descending frequency, by pooled IMR-687 treatment group column, and then alphabetically for ties.

- The number and percentage of subjects reporting each TEAE.
- The number and percentage of subjects reporting common ($\geq 10\%$) TEAEs (i.e., those occurring in at least 10% of subjects in any IMR-687 treatment group)
- The number and percentage of subjects reporting treatment-related TEAEs
- The number and percentage of subjects reporting treatment-related common ($\geq 10\%$) TEAEs

All AEs (including non-treatment-emergent events) recorded on the CRF, all SAEs, and all deaths that occur following the first dose of study drug will be listed. All AE tables and listings will be reported using the safety analysis set.

